### **3.3.2 CHOP-INTEND Infant Motor Function Scale**

The CHOP-INTEND assessment contains 16 items, the total score ranges from worst possible score of 0 to a best possible score of 64

The CHOP-INTEND infant motor function scale total score, change, and percent change from baseline will be summarized by visit.

In addition, the CHOP-INTEND infant motor function scale total score, change, and percent change from baseline to the last available visit for each patient will also be summarized.

The proportion of subjects who achieve improvement in CHOP INTEND total scores will be tabulated by visit. Improvement is defined as at least a four-point increase from baseline. Subjects who die or withdraw from the study prior to a visit will be counted as non-responders for the visit and all subsequent visits and will be included in the denominator for the calculation of the proportion. For subjects on permanent ventilation, because CHOP INTEND assessment continues, functional scores after permanent ventilation will be used to assess improvement in CHOP-INTEND. If a subject misses a visit and has visit(s) beyond the visit, then the subject will be counted as a non-responder and included in the denominator for the calculation of the proportion for the visit.

Subjects who are ongoing in the study and haven't reached a visit will not be included in the denominator for the calculation of the proportion for the visit and all subsequent visits.

The proportion of subjects who achieve improvement in CHOP INTEND total scores at their last available visit will be tabulated. Subjects who die or withdraw from the study will be counted as non-responders and will be included in the denominator for the calculation of the proportion. As a result, mortality will be accounted for in the CHOP INTEND analysis. For subjects on permanent ventilation, because CHOP INTEND assessment continues, functional scores after permanent ventilation will be used to assess improvement in CHOP INTEND.

The above analyses will be tabulated

- 1). by cohort and overall using the Evaluable Population
- 2). by cohort and overall using the 2 SMN2 Copy Set
- 3). by cohort and overall using the Safety Population
- 4). by SMA subtype using the Safety Population

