## 3 ANALYTICAL PLAN

### 3.1 General Overview of Analyses

#### 3.1.1 *Statistical Methods*

Simple descriptive summary statistics, such as n, mean, standard deviation, standard error, median, interquartile range (25th percentile, 75th percentile), minimum, and maximum for continuous variables, and counts and percentages for categorical variables will be used to summarize most data. Where appropriate, *p*-values will be reported. Null hypotheses will be tested using two-sided tests whose Type I error rates are controlled at alpha = 0.05 unless otherwise stated. Since the primary analysis and secondary analyses are not comparative analysis, adjustments for multiplicity of testing will not be used.

Baseline is defined as the last non-missing value prior to the first dose for ISIS 396443 CS3A.

Age (months) at death or permanent ventilation will be calculated using the following SAS code:

```
yrdif(date1,date2,'ACT/ACT')*12
```

Subject demographic (e.g., age, gender, race, etc.) and baseline characteristics (e.g., age at onset of symptoms, age at SMA diagnosis, SMN2 copy number, subtype of SMA [Type IB if onset of symptoms  $\leq$  2 weeks of age, Type IC if onset of symptoms  $>12$  weeks of age], number of hours of BiPAP support, presence/absence of supplemental G-tube or NG tube feeding within 30 days prior to the first dose, etc.) obtained before the first study drug administration will be summarized by cohort and overall using descriptive statistics.

Subject enrollment and disposition will be summarized. Protocol deviations will be listed.

For by-visit data summary, multiple records with the same visit label will be averaged. Unscheduled results will not be included in the summary tables except for determining baseline, but will be presented in data listings.

The presence/absence of supplemental G-tube or NG tube feeding within 30 days prior to the first dose will be manually reviewed by Ionis physicians.

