#### ***3.1.5.2 CHOP-INTEND Total Score***

The CHOP-INTEND assessment contains 16 items, 13 of them are tested on both right side and left side. The item score will be equal to the maximum score of both sides for those 13 items. If the score for one side is missing the item score will be equal to the score of the non-missing side.

If not all tests were performed at a visit, the approach described below will be used for the handling of missing data. Missing data will be imputed on an individual item level. If a test is missing at screening, then the missing test will be imputed as the median of the non-missing values of the group to which the subject belongs: age at symptom onset ( $\leq 2$  weeks,  $>12$  weeks) by disease duration ( $\leq 2$  weeks,  $>12$  weeks). If for the subject with the missing test, the corresponding visit is flanked by visits with non-missing tests, the missing test will be imputed using linear interpolation with the result rounded to the nearest integer score. Otherwise, the missing test will be imputed as the lowest score of the visit in the group (age at symptom onset by disease duration) to which the subject belongs. If the group is empty, the missing test will be imputed as the lowest score of all available subjects of the visit.

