Subjects who die or withdraw from the study will be counted as non-responders and will be included in the denominator for the calculation of the proportion. As a result, mortality will be accounted for in the motor milestone analysis. For subjects on permanent ventilation, because motor milestone assessment continues, functional scores after permanent ventilation will be used to assess improvement in motor milestones.

The primary analysis will be the proportion of subjects who achieve improvement in motor milestones at their last available visit. It will be tabulated by cohort and overall. The primary analysis will be conducted using the Evaluable Population.

As the sensitivity analyses, the proportion of subjects who achieve improvement in motor milestones at their last available visit will be tabulated

- 1). by cohort and overall using the 2 SMN2 Copy Set
- 2). by cohort and overall using the Safety Population
- 3). by SMA subtype using the Safety Population

In addition, the following analyses will also be conducted to assess effects of treatment with ISIS 396443 on the motor milestone improvement over time:

- The proportion of subjects who achieve improvement in motor milestones will be tabulated by visit.

Subjects who die or withdraw from the study prior to a visit will be counted as non-responders for the visit and all subsequent visits and will be included in the denominator for the calculation of the proportion. As a result, mortality will be accounted for in the motor milestone analysis. For subjects on permanent ventilation, because motor milestone assessment continues, functional scores after permanent ventilation will be used to assess improvement in motor milestones.

If a subject misses a visit and has visit(s) beyond the visit, then the subject will be counted as a non-responder and included in the denominator for the calculation of the proportion for the visit.

Subjects who are ongoing in the study and haven't reached a visit will not be included in the denominator for the calculation of the proportion for the visit and all subsequent visits.

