- The proportion of subjects who achieve full head control (defined as All the Time Upright), independent sitting (defined as either Prop, Stable Sit or Pivot), rolling (Prone to Supine or Supine to Prone), crawling (defined as crawling On outstretched hand, flat on abdomen, or On hands and knees), standing (defined as Stands with support or Stands unaided), or walking (Cruising (holding on) or Walking independently) at their last available visit. Subjects who die or withdraw from the study will be counted as non-responders and will be included in the denominator for the calculation of the proportion. For subjects on permanent ventilation, because motor milestone assessment continues, functional scores after permanent ventilation will be used to assess improvement in motor milestones.
- The proportion of subjects who achieve full head control (defined as All the Time Upright), independent sitting (defined as either Prop, Stable Sit or Pivot), rolling (Prone to Supine or Supine to Prone), crawling (defined as crawling On outstretched hand, flat on abdomen, or On hands and knees), standing (defined as Stands with support or Stands unaided), or walking (Cruising (holding on) or Walking independently) will be tabulated by visit. Subjects who die or withdraw from the study prior to a visit will be counted as non-responders for the visit and all subsequent visits and will be included in the denominator for the calculation of the proportion. For subjects on permanent ventilation, because motor milestone assessment continues, functional scores after permanent ventilation will be used to assess improvement in motor milestones.

If a subject misses a visit and has visit(s) beyond the visit, then the subject will be counted as a non-responder and included in the denominator for the calculation of the proportion for the visit. Subjects who are ongoing in the study and haven't reached a visit will not be included in the denominator for the calculation of the proportion for the visit and all subsequent visits.

- Summary of change from baseline in the motor milestone total score at their last available visit. The total motor milestone score equals to the sum of individual scores. For example, if the subject cannot maintain head control this is scored as 0, head wobbles as 1, and all the time upright as 2. Complete inability to perform any motor task will therefore be as zero. The ability to master all motor milestones will be scored as 26.

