- Summary of change from baseline in the motor milestone total score by visit.

The above analyses will be tabulated

- 1). by cohort and overall using the Evaluable Population
- 2). by cohort and overall using the 2 SMN2 Copy Set

- 3). by cohort and overall using the Safety Population
- 4). by SMA subtype using the Safety Population

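### By-visit mean changes in CHOP INTEND and milestone total have no rule for deaths, so by default they describe only infants alive and assessed

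*SAP*

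**What the plan says.** For CHOP INTEND, SAP 3.3.2 states: "The CHOP-INTEND infant motor function scale total score, change, and percent change from baseline will be summarized by visit". It adds a summary of change to each infant's last available visit. For the milestone total, SAP 3.2 lists "Summary of change from baseline in the motor milestone total score by visit" and "Summary of change from baseline in the motor milestone total score at their last available visit". SAP 3.1.1 gives the form of such summaries: "Simple descriptive summary statistics, such as n, mean, standard deviation", followed by the median, quartiles and range. None of these entries says what happens to an infant who has died.

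The responder proportions do have a rule. SAP 3.3.2 says of the by-visit CHOP INTEND proportion: "Subjects who die or withdraw from the study prior to a visit will be counted as non-responders for the visit and all subsequent visits". SAP 3.2 says of the milestone proportion at the last available visit: "Subjects who die or withdraw from the study will be counted as non-responders". In both cases these infants stay in the denominator, and the SAP remarks that mortality is thereby accounted for.

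The imputation rules in SAP 3.1.5.1 and 3.1.5.2 work item by item and begin: "If not all tests were performed at a visit, the approach described below will be used for the handling of missing data".

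**The concern.** The same death is treated in three ways. In a responder table the infant is a failure. In a by-visit mean the infant is absent. In the last-visit mean the infant contributes the change recorded before death, which may be a gain. A reader who meets the remark about mortality in SAP 3.3.2 could take it to cover the means as well, and it does not.

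CHOP INTEND is a named secondary efficacy endpoint, and the by-visit summary is the only CHOP INTEND analysis that Protocol 10.5.2 describes. There is no control arm, so the course over visits invites reading as a drug effect. SAP 3.1.4 intends interim results for regulatory submissions. If infants who die had smaller changes than survivors, part of an upward course reflects who is left in the average.

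**Working it through.** **What enters a by-visit mean.** The death rule is written only for proportions (SAP 3.2, 3.3.2). Imputation starts from an assessment with some items missing. An entirely missed visit is dealt with separately, again only for proportions: "If a subject misses a visit and has visit(s) beyond the visit, then the subject will be counted as a non-responder". Nothing supplies a score for a visit after death, so the default is the mean over infants alive and assessed.

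**The plan's own figures.** The documents state no number for these means. The only power figures are in SAP Table 1, for the primary responder endpoint: n = 20, null rate 5%, two-sided exact test at 0.05. Rejection needs at least 4 responders, since P(X ≥ 4) = 0.0159 and P(X ≥ 3) = 0.0755. Power recomputes to 58.9%, 77.5%, 89.3% and 95.6%, against the stated 58%, 77%, 89% and 95%. The table reproduces, and this point does not touch it.

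**Size of the shift.** Let S be the mean change in survivors, M the mean change in the k infants who died, and D = S − M.

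- Mean over all N infants: [(N − k)S + kM]/N = S − (k/N)D.
- Mean over those alive and assessed: S.
- Inflation: (k/N) × D.

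Inputs: N = 20 (SAP Table 1); Cohort 1 n = 4 (SAP 1.1); CHOP INTEND improvement threshold 4 points (SAP 3.3.2). The values of k and D are assumptions.

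| N | Deaths k | D = 10 | D = 20 |
|---|---|---|---|
| 20 | 2 | 2/20 × 10 = 1.0 | 2/20 × 20 = 2.0 |
| 20 | 4 | 4/20 × 10 = 2.0 | 4/20 × 20 = 4.0 |
| 4 | 1 | 1/4 × 10 = 2.5 | 1/4 × 20 = 5.0 |

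As an example, take S = +10 and M = −5. The by-visit mean is +10 however many have died. The all-infant mean is (18 × 10 − 2 × 5)/20 = +8.5 with 2 deaths and (16 × 10 − 4 × 5)/20 = +7.0 with 4.

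**Simulation check.** N = 20, 4 deaths, with the infants removed chosen on a marker correlated with change. With an assumed SD of change of 10 points, the mean rises by 0 if death is unrelated to change, by 1.7 at correlation 0.5, and by 3.3 if the four smallest changes are lost. With SD 6 the last two figures are 1.0 and 2.0; with SD 14 they are 2.3 and 4.7.

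The formula also holds for the milestone total, with D on that 26-point scale, so the point values above apply to CHOP INTEND only.

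**The case against.** The strongest reply is that mortality is already on view. The responder tables count deaths as failures by visit and at last visit, in the same populations as the means. Kaplan-Meier event-free survival is tabulated in those populations too (SAP 3.3.1). The n and the median are already planned. The means are descriptive, SAP 3.1.1 calls the primary and secondary analyses non-comparative, and no decision rule uses the means. All of this stands, and it limits the point to a modest addition. It does not remove it: the survival curve runs by age rather than study visit, and n alone does not separate deaths from withdrawals, missed visits and visits not yet reached.

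A reader might infer more than the documents support:

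- *That losing the weakest infants must raise mean change.* Change is measured within each infant. The mean rises only if those who died had smaller changes, not merely lower scores.
- *That deaths will be frequent here and tied to motor score.* Protocol 2.1 says the most severe form is usually fatal by age 2. That is natural history, with no rate under treatment and no link between score and death.
- *That the SAP deliberately excludes deaths.* It is silent. Stretching the lowest-score fallback in SAP 3.1.5.2 to visits after death would give a dead infant a living infant's score, which changes the problem without solving it.
- *That scoring death as 0 shows the size of the bias.* With survivors at +10 and 4 deaths in 20, a zero score gives (160 − 4 × 15)/20 = +5.0, (160 − 4 × 25)/20 = +3.0 or (160 − 4 × 35)/20 = +1.0 for assumed baselines of 15, 25 and 35. That spread comes from the scoring rule, which penalises a stronger baseline more. Zero is also a score a living infant can have.

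**Conclusion.** The gap is real and moderate. For N = 20 the inflation of mean CHOP INTEND change is 1 to 2 points with 2 deaths and 2 to 4 points with 4, if D lies between 10 and 20. The upper end equals the SAP's improvement threshold. It is zero if death is unrelated to change. These sizes rest on assumed k and D, since the documents give neither. The inconsistency at the last available visit needs no assumption about size: one table keeps a pre-death change for an infant whom its companion counts as a failure. The primary responder analysis is not affected. The change is worth making because it is cheap and these tables report a secondary endpoint in an uncontrolled trial.

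**What to change.** Keep the planned tables and make three additions.

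1. Label the by-visit summaries of CHOP INTEND and milestone total as describing infants alive and assessed.
2. In each by-visit row, show cumulative deaths and cumulative withdrawals beside n. The by-visit CMAP summaries in SAP 3.3.3 have the same gap and could carry the same counts.
3. Add a sensitivity median with quartiles of change, by visit and at the last visit, in which infants who died rank below every observed value. No numeric score is assigned; where a quartile or the median falls among the deaths, report it as death.

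At an interim cut, count a dead infant at a visit only if that infant's scheduled date for the visit precedes the cut. Otherwise dead infants would appear at late visits from which living infants are excluded for not having reached them.

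The cost is a few extra rows from data already collected, and sensitivity figures that will look less favourable than the planned ones.

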### **3.3.3 CMAP Ulnar and Peroneal Nerves**

CMAP is an electrophysiological measure used to determine the approximate number of motor neurons in a muscle or group of muscles. CMAP amplitude and CMAP area will be evaluated at two sites, right side ulnar nerve and right side peroneal nerve.

The absolute values for CMAP amplitude and CMAP area, as well as changes and percent changes from baseline will be summarized by visit.

In addition, the absolute values for CMAP amplitude and CMAP area, as well as changes and percent change from baseline to the last available visit for each patient will also be summarized.

The proportion of subjects with a change from baseline CMAP amplitude at the peroneal nerve greater than 0.5 mV will be tabulated by visit. Subjects who die or withdraw from the study prior to a visit will be counted as non-responders for the visit and all subsequent visits and will be included in the denominator for the calculation of the proportion. As a result, mortality will be accounted for in the CMAP analysis. For subjects on permanent ventilation, because CMAP assessment continues, the scores after permanent ventilation will be used to assess improvement in CMAP. If a subject misses a visit and has visit(s) beyond the visit, then the subject will be counted as a non-responder and included in the denominator for the calculation of the proportion for the visit. Subjects who are ongoing in the study and haven't reached a visit will not be included in the denominator for the calculation of the proportion for the visit and all subsequent visits.

The proportion of subjects with a change from baseline CMAP amplitude at the peroneal nerve greater than 0.5 mV at their last available visit will be tabulated. Subjects who die or withdraw from the study will be counted as non-responders and will be included in the denominator for the calculation of the proportion. As a result, mortality will be accounted for in the CMAP analysis. For subjects on permanent ventilation, because CMAP assessment continues, the assessments after permanent ventilation will be used to assess improvement in CMAP.

The above analyses will be tabulated

- 1). by cohort and overall using the Evaluable Population
- 2). by cohort and overall using the 2 SMN2 Copy Set
- 3). by cohort and overall using the Safety Population
- 4). by SMA subtype using the Safety Population

- 4). by SMA subtype using the Safety Population.

#### **3.4.2 Growth Parameters**

The growth parameters will include weight to age ratio, weight to length ratio, head circumference, chest circumference, head to chest circumference ratio, arm circumference, and weight for age percentile, height for age percentile, and head circumference percentile using the WHO child growth standards (WHO Child Growth Standards, 2006). The absolute values as well as changes, and percent changes from baseline will be summarized by visit.

The above analyses will be tabulated

- 1). by cohort and overall using the Evaluable Population
- 2). by cohort and overall using the 2 SMN2 Copy Set
- 3). by cohort and overall using the Safety Population
- 4). by SMA subtype using the Safety Population.

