### **5. SUBJECT ELIGIBILITY**

#### **5.1 Inclusion Criteria**

To be eligible to participate in this study candidates must meet the following eligibility criteria at screening.

1. Signed informed consent of parent(s) or guardian(s)
2. Genetic documentation of 5q SMA homozygous gene deletion or mutation
3. Onset of clinical signs and symptoms consistent with SMA at  $\geq 21$  days and  $\leq 6$  months (180 days) of age
4. Males and females between  $\geq 21$  days and  $\leq 7$  months (210 days) of age at Screening
5. At study entry, receiving adequate nutrition and hydration (with or without gastrostomy), in the opinion of the Site Investigator
6. Body weight  $> 5^{\text{th}}$  percentile for age using CDC guidelines
7. Medical care meets and is expected to continue to meet guidelines set out in the Consensus Statement for Standard of Care in SMA (Wang et al. 2007), in the opinion of the Site Investigator
8. Gestational age of 35 to 42 weeks and gestation body weight  $\geq 2$  kg
9. Reside within approximately 9 hours ground-travel distance from a participating study center for the duration of the study. Residence  $> 2$  hours ground-travel distance from a study center must obtain clearance from the Site Investigator and the study Medical Monitor
10. Able to complete all study procedures, measurements and visits and parent or guardian/subject has adequately supportive psychosocial circumstances, in the opinion of the Site Investigator

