### **6.2.8     *Growth Parameters***

Subjects will be assessed by growth measurements according to the schedule as shown in Appendix A (Schedule of Procedures). Growth parameters of body length, head circumference, chest circumference, and arm circumference will be measured. Additional parameters of weight for age, weight for length, and head to chest circumference ratio will be calculated.

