### **1.3.3 *Exploratory Endpoints***

The following efficacy evaluations will be performed as exploratory endpoints:

- Measures of respiratory status (number of respiratory events, respiratory infections, respiratory-related hospitalizations, ventilator use and O2 saturation awake)
- Growth parameters (weight for age/length, head circumference, chest circumference, head to chest circumference ratio, arm circumference)

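### Among otherwise sound growth measures, SAP 3.4.2 includes a weight-to-age ratio that falls with age by construction, percent changes of percentiles, and no reference-based weight for length

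*SAP*

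**What the plan says.** Protocol 6.2.8 lists the measured growth parameters and then says: "Additional parameters of weight for age, weight for length, and head to chest circumference ratio will be calculated". The word ratio is attached only to the two circumferences; weight is given for age and for length. SAP 1.3.3 uses the same terms and places growth under this introduction: "The following efficacy evaluations will be performed as exploratory endpoints".

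SAP 3.4.2 specifies the analysis: "The growth parameters will include weight to age ratio, weight to length ratio, head circumference, chest circumference, head to chest circumference ratio". The same sentence goes on to list "weight for age percentile, height for age percentile, and head circumference percentile using the WHO child growth standards". One rule then covers every item: "The absolute values as well as changes, and percent changes from baseline will be summarized by visit". The tables are to be produced by cohort and overall in the Evaluable Population, the 2 SMN2 Copy Set and the Safety Population, and by SMA subtype in the Safety Population. No test, threshold or decision is attached to growth.

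**The concern.** The question for growth is whether a child keeps up with children of the same age or length. Three of the planned outputs do not answer it well.

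- **Weight divided by age.** Age multiplies over the study and weight cannot keep pace, so the ratio falls even in a child who stays on the same percentile. The size of the fall depends on age at entry, which varies about elevenfold (21 to 231 days), so a cohort or subtype mean mixes children with very different expected falls.
- **Percent change of a percentile.** The same shift relative to peers gives a large percentage near the bottom of the scale and a small one near the top.
- **Weight for length.** Only a raw ratio is planned. It rises whenever weight grows proportionally faster than length, so a rise does not show that the child has gained weight relative to peers of the same length.

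At stake is the reading of the growth tables, which could show a decline in children who are growing normally, or a mean gain produced by one or two low starters.

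**Working it through.** The plan gives no numerical target for growth, so there is no figure to reproduce. Two direct checks were made.

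**Check 1: weight-to-age ratio**

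Inputs from the documents:
- Age at screening is 21 days up to "months (210 days) of age at Screening" (Protocol 5.1).
- The first dose is at most 21 days after screening (Protocol 3.4.1), so the upper limit of age at first dose is 210 + 21 = 231 days.
- Baseline is the last value before the first dose (SAP 3.1.1).
- Day 253 is 252 days after Day 1.

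The ratio stays constant only if weight rises by the same factor as age, (a + 252)/a, where a is age in days at entry:
- a = 21: 273/21 = 13.0
- a = 231: 483/231 = 2.1

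Screening ends on Day -1, so a child screened at 21 days is at least 22 days old on Day 1. The factor is then 274/22 = 12.5, which changes nothing of substance.

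The direction follows from algebra. With birth weight W0 and a constant gain g per month, W/A = g + W0/A, which falls with age for any W0 above zero. A gain that slows with age gives a fall as well. Protocol 5.1 requires a birth weight of at least 2 kg, so at 30.4375 days per month the W0/A term alone is at least 2/(21/30.4375) = 2.90 kg/month at 21 days and at least 2/(273/30.4375) = 0.22 at Day 253.

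For a sense of size, assume a birth weight of 3.3 kg and a gain of 0.3 to 0.7 kg/month. These values are assumptions, not figures from the documents. One case in full, with g = 0.5 and entry at 120 days:
- Baseline: 3.94 months, 3.3 + 0.5 × 3.94 = 5.27 kg, ratio 1.34.
- Day 253: 372 days = 12.22 months, 3.3 + 0.5 × 12.22 = 9.41 kg, ratio 0.77.
- Change: 0.77/1.34 − 1 = about −42%.

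Over the assumed range of gain:

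| Age at entry | Change by Day 253 | Change by Day 1352, if growth is recorded then |
|---|---|---|
| 21 days | −81% to −87% | −86% to −93% |
| 120 days | −37% to −50% | −50% to −68% |
| 231 days | −20% to −31% | −33% to −51% |

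Entry age moves the result far more than the assumed rate of gain does.

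**Check 2: percent change of a percentile**

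For a starting percentile p and a shift d in SD units, the percent change is 100 × [Φ(z(p) + d)/p − 1], where z(p) is the normal quantile. With d = +0.5:

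| Start | End | Change in points | Percent change |
|---|---|---|---|
| 1st | 3.4 | +2.4 | +239% |
| 6th | 14.6 | +8.6 | +143% |
| 50th | 69.1 | +19.1 | +38% |
| 90th | 96.3 | +6.3 | +7% |

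Effect on a group mean:
- Suppose one child moves +0.5 SD from the 6th percentile (+143%, +8.6 points) and another −0.5 SD from the 75th (−24%, −18.1 points). The mean z change is 0 and the mean percentile change is about −4.7 points, yet the mean percent change is about +59%.
- In Cohort 1, with 4 subjects, one child gaining 0.5 SD from the 6th percentile and three unchanged give 143/4 = about +36%.

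The entry floor, above the 5th "percentile for age using CDC guidelines", applies to weight only. Height and head circumference have no floor, so smaller starting values are possible there.

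**The case against.** The strongest reply is that the same SAP sentence already plans the right measures. WHO percentiles for weight, height and head circumference, with their values and simple changes, show directly whether growth keeps up with age. That stands. A reader might infer from the ratios that growth is analysed only through distorted measures, or that the SAP has replaced weight for age by a quotient. The documents do not support either reading: the weight-for-age percentile is planned beside the ratio, and the protocol names no reference standard.

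A reader might also infer that percent change of a percentile is unrelated to growth relative to peers. It is not. For each child it has the same sign as the shift relative to peers; only its size, and hence the group mean, is distorted. The median and interquartile range planned in SAP 3.1.1 reduce this problem without removing it.

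It could be said that the weight-to-age ratio is a loose name for weight for age. That is unlikely, because the weight-for-age percentile is listed separately in the same sentence.

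Finally, value, change and percent change is a stock formula in this SAP, and growth is exploratory. Both are true. They limit the consequence but do not make the three outputs informative. Nothing here faults percent change for the head, chest or arm circumference. The use of CDC percentiles for eligibility and WHO percentiles for analysis is not a contradiction, since the two serve different purposes.

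**Conclusion.** The point holds in a limited form. The planned WHO percentiles and their simple changes measure growth relative to peers and should stay. The weight-to-age ratio adds nothing to them and will show decline in normally growing infants: the 13-fold and 2.1-fold thresholds follow from the documents' own ages and days, while the percentage falls rest on the assumed birth weight and gain. Percent change of percentiles gives +143%, +38% or +7% for one and the same 0.5 SD shift; this assumes only that percentiles map to z-scores through the normal distribution. Weight for length, named in Protocol 6.2.8 and SAP 1.3.3, has no reference-based measure at all, and this is the one real gap in coverage. No primary or secondary conclusion is affected.

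**What to change.** In SAP 3.4.2:

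1. Delete the weight-to-age ratio.
2. Replace the weight-to-length ratio with a WHO weight-for-length z-score or percentile.
3. For the reference-based measures (weight for age, height for age, weight for length, head circumference), report the value and the absolute change from baseline, preferably as z-scores, on which equal shifts count equally wherever a child starts.
4. Drop percent change for percentiles only, and keep it for the raw circumferences if wanted.

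The weights, lengths and circumferences are already collected, and the SAP already applies the WHO standards to three measures. The cost is reprogramming the growth tables, with no change to visits or data collection. The choice between z-scores and percentiles is a preference; items 1, 2 and 4 carry the point.
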